9.1. Investigator/Investigation Site Selection

The PI will provide oversight for the entire study team at his/her site, implement and manage the day-to-day conduct of the clinical study, ensure data integrity, and the rights, safety, and well-being of the subjects involved in the clinical study.

The PI shall:

- Be qualified by education, training, and experience to assume responsibility for the proper conduct of the clinical study.
- Be qualified practitioners and experienced in the management of post-MI subjects
- Be able to comply with applicable Institutional Review Board (IRB)/Ethics Committee (EC) and regulatory requirements
- If applicable, not to be debarred, disqualified, or working under sanctions in applicable regions

Additionally, the site:

- Has the required number of eligible subjects needed within the recruitment period
- Has one or more qualified Investigators, a qualified study team, and adequate facilities for the foreseen duration of the clinical study
- Needs to have specialized practitioners (e.g. Interventional Cardiologist and Electrophysiologist) to participate in the study and be complaint with this study protocol.

9.2. Site Initiation

During the initiation process (prior to subject enrollment), Medtronic will provide clinical study materials (e.g. Investigator Site File, database access codes etc.) and train site personnel on the Clinical Investigation Plan (CIP), relevant standards and regulations (if needed), informed consent, and data collection and reporting tools.

A Clinical Trial Agreement (CTA) shall be entered into effect by Medtronic, the participating investigation site and/or the Principal Investigator (PI) at each investigation site (per the local legal requirements), and returned, fully executed, to Medtronic prior to the commencement of any study activities. Financial aspects of conducting and reporting a study will be specified in the agreement. By signing and dating the agreement, the Investigator indicates compliance to the CIP.

Prior to performing study related activities, all sites must have IRB/EC approval, as applicable for that geography.

All local and regional regulatory requirements must be fulfilled prior to site initiation and enrollment of subjects into the study. Each study site must have written documentation of site and Investigator initiation before beginning any study-related activities. Requirements for initiation vary by geography, and may include, but are not limited to:

- Written documentation of EC approval of the current versions of the CIP and IC Form (approved versions must be retrievable from the IRB/EC approval letter or submission letter) and the corresponding voting list (as required per local law)

- Regulatory authority approval or notification (as required per local law)
- Executed CTA on file with Sponsor
- Current Curriculum Vitae (CV) of Investigators and key members of the investigation site team
- Documentation of delegated tasks
- Documentation of study site personnel training

Additional requirements imposed by the EC and regulatory authority shall be followed, if appropriate. Medtronic will provide each study site with documentation of study site/Investigator initiation; this letter must be received prior to subject enrollment. If new members join the study site team after site initiation, they will receive training on the applicable clinical study requirements relevant to their roles before contributing to the clinical study. Medtronic will provide the study site with documentation of the investigation site team initiation upon receipt of all required documentation.

In addition, all participating site staff must be trained on the current version of the CIP pertinent to their role in the study and must be delegated by the principal investigator to perform study related activities, which must be documented on the Delegated Task List. Site personnel performing only standard of care procedures and no study related activities throughout the study (including but not limited to ICD/ CRT-D implant) do not need to be trained on the CIP and delegated on the Delegated Task List.

9.3. Schedule of Events

Clinical data will be collected at the Baseline 3 month, 6 month, 12 month, and exit visits. In addition if applicable, clinical data will be collected with an exit or death, as well as unscheduled visits. Device data will be collected from device interrogations on Medtronic devices received during the period between the enrollment and exit until study closure; for non-Medtronic devices, device data will not be collected. Data will be collected using eCRFs using an electronic data management system for clinical studies. In addition to eCRF data, non-eCRF data will be collected including device interrogation files (for Medtronic implanted devices only). Surveys may also be used throughout the study.

Data will be stored in a secure, password-protected database, which will be backed up nightly. Data will be reviewed using programmed and manual data checks. Data queries will be made available to study sites for resolution. Study management reports will be generated by Medtronic to monitor data quality and study progress. At the end of the study, the data will be frozen and retained indefinitely by Medtronic. Data Collection requirements are summarized in the table 2 below.

Table 2 Data Collection and study procedure requirements at subject visit

Study Procedure	Baseline	3 month visit	6 month visit	12 month visit	Study Exit
Patient informed consent	X				
Eligibility Verification (Inclusion/ exclusion assessment)	X				
Subject Demographics	X				
Acute MI information	X				
Medical History	X				
Cardiovascular Medications	X	X			
LVEF measurement	X	X*	X (collect if performed as per SOC)	X (collect if performed as per SOC)	
ECG	X	X (collect if performed as per SOC)	X (collect if performed as per SOC)	X (collect if performed as per SOC)	
Referral Status		X	X	X	X
Implant Status (if applicable)		X (if subject receives or has received device implant)	X (if subject receives or has received device implant)	X (if subject receives or has received device implant)	X (if subject receives or has received device implant)
Device Interrogation File (pdd) or CareLink Transmission for subjects implanted with Medtronic device only		X	X	X	X
Adverse Event	As they occur				
System Modification					
Study Deviation					
Subject Death					

* The LVEF measurement needs to be performed ≥ 40 days post-acute MI for MI subjects without revascularization, or ≥ 90 days post-revascularization for post-MI subjects with revascularization done.

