9.6.1. Information Collected

The following information is required to be collected at follow-up visits:

- Referral status
- Implant status
- Cardiovascular Medication categories as listed under Enrollment/ Baseline (for 3-month visit only)

- LVEF measurement as per standard practice.
 - For 3-month visit, the LVEF measurement needs to be performed ≥ 40 days post-acute MI for MI subjects without revascularization, or ≥ 90 days post-revascularization for post-MI subjects with revascularization done.
- ECG as per standard practice
- Cardiovascular Adverse events, Study Deviations and System Modification.

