7.9.3.3 Analysis methods

At each follow-up visit (3 months, 6 months, 12 months), the proportion of subjects who received an ICD/CRT-D will be computed.

The numerator will be the number of subjects who were implanted at a given follow up visit. In the Implant CRF, these subjects will have answer “yes” to the question “Has the subject received an ICD or CRT-D?”.

The denominator will be either the Enrolled Population or a composite of the below:

- (a) ***all patients meeting an indication for implant and not having been implanted at the previous visits.*** That is, within the Implant CRF form, all subject that at any previous visits will have answer “yes” to the question “did the subject meet an indication for an ICD or CRT-D?”, and at all previous visits will have answer “no” to the question “has the subject received an ICD or CRT-D?”
- (b) ***all patients meeting an indication for implant at the given visit.*** That is, within the referral CRF form, all subject that at a given visit will have answer “yes” to the question “did the subject meet an indication for an ICD or CRT-D?”

A SAS code similar to the example SAS code shown in Section 7.9.1.3 will be used. Separately for each follow up visit, the results will be shown in a table similar to Table 6 below, where “Indicated for an ICD/CRT-D” is the denominator above.

Table 6: Proportion (95% CI) of subjects who receive ICD/CRT-D at visit X

	Enrolled Population		Indicated for an ICD/CRT-D Population	
Region	n/N (%)	95% CI	n/N (%)	95% CI
Region 1	XX/XX (XX.XX%)	(XX.XX% - XX.XX%)	XX/XX (XX.XX%)	(XX.XX% - XX.XX%)
Region 2	XX/XX (XX.XX%)	(XX.XX% - XX.XX%)	XX/XX (XX.XX%)	(XX.XX% - XX.XX%)
...
Overall	XX/XX (XX.XX%)	(XX.XX% - XX.XX%)	XX/XX (XX.XX%)	(XX.XX% - XX.XX%)

In addition to the above analyses, logistic regression models similar to the example model in Section 7.9.1.3 might be fitted overall and by region, to estimate the odds ratios of being implanted, depending on different factors, such as age, gender, specialty of physician who implanted, type of device received – ICD or CRT-D, PCI versus non-PCI, STEMI versus non-STEMI. Results will be displayed either by means of either tables or of plots.

Additional analysis:

A competing risk event curve with accompanying 95% confidence bounds and mortality accounted for, will be produced for each region, to assess a subject's time from enrollment to:

- (a) Having met the referral criteria;
- (b) Having been referred;

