7.9.5.3 Analysis methods

At each visit, the reasons for refusing referral (“reasons the subject has not been referred at this visit” in the referral CRF) at each visit will be summarized as displayed in table 8.

Table 8: Reason of referral

Region	Reason for refusal referral	3 months visit	6 months visit	12 months visit
Region 1	Reason 1 Reason 2 ... Reason n	XX/XX (XX.XX%) XX/XX (XX.XX%) ... XX/XX (XX.XX%)	XX/XX (XX.XX%) XX/XX (XX.XX%) ... XX/XX (XX.XX%)	XX/XX (XX.XX%) XX/XX (XX.XX%) ... XX/XX (XX.XX%)
...	Reason 1 Reason 2 ... Reason n
Overall	Reason 1	XX/XX (XX.XX%)	XX/XX (XX.XX%)	XX/XX (XX.XX%)

	Reason 2 ... Reason n	XX/XX (XX.XX%) ... XX/XX (XX.XX%)	XX/XX (XX.XX%) ... XX/XX (XX.XX%)	XX/XX (XX.XX%) ... XX/XX (XX.XX%)
--	-----------------------------	---	---	---

Further, at each visit, among all subjects that were recommended for ICD/CRT-D (ie: answer “yes” to question “did the subject meet an indication for an ICD or CRT-D” in the implant CRF), the proportion of those who refused implant (answer “yes” to the question “did the subject refuse the implant”) will be computed and displayed. The reasons for implant refusal (“reason for implant refusal” in implant CRF) will then be computed and displayed in a table similar to Table 7 above.

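### Protocol Table 2 limits implant status to subjects with a device, contradicting Protocol 9.6.1 and the SAP; followed literally, it may leave implant refusers and indicated, non-implanted subjects without a form

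*Protocol*

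**What the plan says.** Protocol 9.3 introduces its schedule with "Data Collection requirements are summarized in the table 2 below". In that table the Implant Status row is labelled as applying where applicable, and each of its four cells (3, 6 and 12 months, and exit) carries the condition "X (if subject receives or has received device implant". The Referral Status row directly above has a plain mark in the same four columns.

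Protocol 9.6.1 opens its list with "The following information is required to be collected at follow-up visits" and includes "Implant status" with no condition about having a device.

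The SAP draws on the Implant CRF in two places that concern subjects without a device:

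- SAP 7.9.3.3, denominator part (a), counts "all patients meeting an indication for implant and not having been implanted at the previous visits". The rule begins "within the Implant CRF form, all subject that at any previous visits will have answer", and requires a yes to indication at a previous visit together with a no to device received at all previous visits.
- SAP 7.9.5.3 defines the subjects recommended for a device by the indication item on the Implant CRF. Among them it computes "the proportion of those who refused implant", and takes the reasons for refusal from the same form.

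SAP 7.9.3.3, part (b), places the same indication question, for the current visit, on the referral CRF.

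**The concern.** Under Table 2, completion of the form depends on the outcome being measured. The subjects who fall under the condition are those who received a device. Those the SAP needs in order to describe the gap between indication and implantation are the ones who did not. A site that leaves out the form for a subject who was found indicated and declined is following the schedule, so the omission need not surface as a deviation.

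Three secondary outputs are exposed: the implanted proportion among indicated subjects, the implant-refusal proportion with its reasons, and possibly the proportion indicated. Protocol 4.1 gives low ICD use among indicated patients as a motivation for the study, so these outputs are close to its purpose. The analysis would not correct the loss: Protocol 12.5 rules out imputation, and SAP 7.4 says the main analyses will not account for missing data. Protocol 9.7 ends data collection at exit, so reasons for refusal become harder to recover later.

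**Working it through.** The plan states no figure to reproduce. The check sets the passages side by side and then sizes the worst case.

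**Step 1: what each output needs, and what Table 2 supplies.**

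| Output | Needs an Implant form from subjects without a device? | Effect if Table 2 is followed literally |
|---|---|---|
| Implanted / enrolled (SAP Table 6, first column) | No | None |
| Implanted / indicated (SAP Table 6, second column) | Yes, for part (a), and for part (b) if the item is on the Implant CRF | Toward 100% |
| Implant refusal and reasons (SAP 7.9.5.3) | Yes | Refusals toward 0 |
| Indicated / enrolled (SAP Table 5) | Only if the indication item is solely on the Implant CRF | Too low |
| Reasons for non-referral (SAP 7.9.5.3) | No; taken from the referral CRF | None |
| Primary endpoint (SAP 7.9.1.3) | No; taken from the referral CRF | None |

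**Step 2: does another passage supply the data?**

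- Protocol 9.6.1 does so for follow-up visits, if sites follow it rather than Table 2. It does not cover exit, and the exit list in Protocol 9.7 does not mention implant status.
- SAP 7.9.3.3(b) would preserve indication at the current visit if the item is on the referral CRF. Part (a) would still lose subjects carried over from earlier visits, because it needs a recorded no on the Implant CRF. Refusal and its reason would still be lost, since the SAP places them only on the Implant CRF.
- That backup is itself uncertain after referral. Protocol 9.6 ties the Referral Status form at later visits to subjects not yet referred, whereas Table 2 marks it at every visit.

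**Step 3: direction of the bias.** Let *u* be the true implanted share of indicated subjects, and *f* the share of indicated, non-implanted subjects for whom an Implant form is completed. If indication is read only from that form, the reported proportion is

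u / [u + (1 − u) f].

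At f = 1 this equals u. At f = 0 it equals 1 for any u above 0. For u strictly between 0 and 1, any f below 1 overstates u.

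**Step 4: size at f = 0.** The documents give no indication rate, so 25 indicated subjects per region is an assumption. The values of u are the ICD-use figures in Protocol 4.1: 12% (Asia), 24% (Europe) and 30 to 50% (USA). Counts are rounded to whole subjects (7.5 to 8 and 12.5 to 12). Intervals are two-sided 95% Wilson.

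| u | Complete collection | Table 2 followed literally | Without a form |
|---|---|---|---|
| 12% | 3/25 = 12% (4.2 to 30.0%) | 3/3 = 100% (43.9 to 100%) | 22 (88%) |
| 24% | 6/25 = 24% (11.5 to 43.4%) | 6/6 = 100% (61.0 to 100%) | 19 (76%) |
| 30% | 8/25 = 32% (17.2 to 51.6%) | 8/8 = 100% (67.6 to 100%) | 17 (68%) |
| 50% | 12/25 = 48% (30.0 to 66.5%) | 12/12 = 100% (75.8 to 100%) | 13 (52%) |

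**Step 5: a second set of assumptions, from the SAP's planning figures.** SAP 6.1 plans for 54 subjects with a reason for referral per region, 70% of them referred: 54 × 0.70 = 37.8, about 38. Assume half are indicated (19) and 40% of those implanted (7.6, about 8). Implanted among indicated is 8/19 = 42%, against 8/8 = 100% as collected. Indicated among the planned 200 enrolled is 19/200 = 9.5%, against 8/200 = 4% if the item is only on the Implant CRF. The other 19 − 8 = 11 subjects, and any refusal reasons they gave, are missing.

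**The case against.** The strongest reply is that this is loose wording in one table and that no data need be lost. Protocol 9.6.1 requires implant status at follow-up without condition, and nothing ranks Table 2, which is introduced as a summary, above the text. The items the SAP cites, such as a no to device received and a refusal with its reason, make sense only for subjects without a device. The SAP was released in June 2019, after the first enrollment in November 2018, so it is probably describing a form already in use and meant for such subjects. Part (b) of SAP 7.9.3.3 suggests that indication may also be on the referral form. The CRFs are held under separate cover (Protocol Appendix A), so it is an inference that the Table 2 row is the SAP's Implant CRF.

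All of that stands, and it limits the conclusion. A reader might infer that indicated subjects without a device, and all refusers, will certainly go unrecorded. The documents do not support that. Loss depends on sites following Table 2 rather than 9.6.1, and subjects who are not referred have their reasons recorded on the referral CRF. A reader might also infer that the whole implant objective fails, but implanted among enrolled needs forms only from subjects with a device.

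The reply does not remove the contradiction. Two protocol sections give sites different instructions for the same item, and the instruction in the schedule is the one that defeats the SAP's definitions. If the form was meant for subjects without a device, Table 2 tells sites the wrong thing.

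**Conclusion.** The contradiction between Protocol Table 2 on one side and Protocol 9.6.1 with SAP 7.9.3.3(a) and 7.9.5.3 on the other is established from the text. The data loss is conditional. Where Table 2 is followed literally, implanted among indicated is biased toward 100% and recorded implant refusals toward 0. The proportion indicated is understated only if the indication item sits solely on the Implant CRF, a point on which the SAP disagrees with itself.

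In the worst case, with ICD use of 12 to 50% among indicated subjects, about half to nearly nine-tenths of them would have no Implant form. That range takes the background ICD-use figures as a guide to this study and assumes no form for any non-implanted subject. The counts of 25 and 19 indicated subjects, and the 40% implanted in the second illustration, are assumptions too. The affected outputs are descriptive and secondary.

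**What to change.** - In Protocol Table 2, remove the device condition from the Implant Status row. Require the form at each visit and at exit, at least for every subject referred, seen for SCD risk stratification or meeting an indication, whether or not implanted. Make 9.6.1, the exit list in 9.7 and the CRF completion guideline agree.
- In SAP 7.9.3.3 (a) and (b) and 7.9.5.3, name one CRF as the source of the indication item.
- Query every subject already referred or assessed who has no Implant form, before exit where possible.

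The cost is slightly more site data entry on a form that already exists, plus the queries. The Table 2 change is a protocol revision, so it goes through the approvals in Protocol 14.6. It changes no clinical care. Limiting the requirement to the subjects listed above avoids forms for those who were never referred, assessed or indicated.

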9.4. Subject Consent

Informed consent is defined as a legally effective documented confirmation of a patient's voluntary agreement to participate in a particular clinical study after the information has been given to the patient on all aspects of the clinical study that are relevant to the patient's decision to participate. This process

includes obtaining an Informed Consent Form (IC Form) and an Authorization to Use and Disclose Personal Health Information/Research Authorization/other privacy language (data protection authorization) as required by law that has been approved by the study site's IRB/EC, and Medtronic, and personally signed and dated by the patient and the PI or an authorized designee.

Prior to enrolling patients, each site must have documented IRB/EC approval of the IC Form (and data protection authorization, where applicable) as required by law. Any changes to a previously approved IC Form throughout the course of the study must be reviewed and approved by Medtronic and the IRB/EC reviewing the application before being used to obtain consent or re-consent a study subject. The document(s) must be controlled (i.e. versioned and dated) to ensure it is evident which version(s) were approved by Medtronic and the IRB/EC. All important new information should be provided in written form to new and existing subjects throughout the study. If relevant, all affected subjects must be asked to confirm their continuing informed consent in writing.

Prior to initiation of any study-specific procedures, informed consent must be obtained from the patient. Likewise, privacy or health information protection regulation may require patients to sign additional forms to authorize sites to submit subject information to the study sponsor. Obtaining informed consent must be conducted by the PI or an authorized designee, and the IC Form and a data protection authorization, as required by law, must be given to the patient in a language he/she is able to read and understand.

The process of obtaining informed consent shall:

- Ensure that the PI or an authorized designee conducts the informed consent process.
- Include all aspects of the clinical study that are relevant to the patient's decision to participate throughout the clinical study.
- Avoid any coercion or undue improper influence on, or inducement of the patient to participate.
- Not waive or appear to waive the patient's legal rights.
- Ensure the IC Form and a data protection authorization as required by law, are given to the patient in a non-technical language the patient is able to read and understand.
- Provide ample time and opportunity for the patient to read and understand the Informed Consent Form to inquire about details of the study, and to consider participation. All questions about the study should be answered to the satisfaction of the patient.
- Include a personally dated signature of the subject acknowledging that their participation in the study is voluntary.
- Include a personally dated signature by the PI, or authorized designee responsible for obtaining the informed consent, as required by local law.
- Provide the subject with a copy of the IC Form and a data protection authorization as required by law.
- Ensure subjects are notified of any significant new findings about the study that become available during the course of the study which are pertinent to the safety and well-being of the subject, as this could impact a subject's willingness to participate in the study.

If the informed consent is obtained the same day the subject begins participating in study-related procedures, it must be documented that consent was obtained prior to participation in any study-related procedures. It is best practice for the process of obtaining the informed consent to be documented in the subject's case history, regardless of circumstance.

In the event the subject cannot read and/or write, witnessed (impartial third party) informed consent will be allowed, provided detailed documentation of the process of obtaining the informed consent is recorded in the subject's case history and the witness signs and dates the Informed Consent Form. Informed consent shall be obtained through a supervised oral process. An impartial witness must be present throughout the process. The IC Form and any other information must be read aloud and explained to the prospective subject if allowed by local law. The witness signs and personally dates the IC Form attesting that the information was accurately explained and that informed consent was freely given. Whenever possible, the subject should "make his mark" (sign or otherwise physically mark the document so as to indicate consent) on the IC Form as well. The IC Form should document the method used for communication with the prospective subject and the specific means by which the prospective subject communicated agreement to participate in the study.

The original of the signed IC Form must be filed in the hospital/clinical chart and/or with the subject's study documents.

The IC Form and a data protection authorization as required by law must be available for monitoring, auditing, and regulatory inspections.

